5.2.1. Analyses for Binary Endpoints

Binary data at each scheduled visit will generally be analyzed by two approaches: (1) the test of hypothesis (and the p-value) of no difference between two treatment groups will be conducted by the Cochran-Mantel-Haenszel (CMH) statistic adjusting for baseline disease severity (IGA = 3 or IGA = 4); p-values from the CMH statistic will be used to test the hypothesis of no difference in binary responses between two treatment groups; and (2) the proportion of responders in each treatment group will be reported and differences between two treatment groups will be summarized by the weighted difference and its 95% confidence interval obtained by normal approximation. The difference in proportions will be calculated within each randomization stratum. The final estimate of the difference in proportions will be a weighted average of these stratum-specific estimates using CMH weights. The CMH weight w_k for stratum k ($k = 1, 2$) is given by,

$$w_k = \frac{\frac{n_{ik} n_{ck}}{n_{ik} + n_{ck}}}{\sum_{j=1}^2 \frac{n_{ij} n_{cj}}{n_{ij} + n_{cj}}}$$

where n refers to sample size, the subscript c refers to a comparator group (eg, placebo) and the subscript i refers to a test group (eg, an active treatment group). The difference is estimated as $\hat{d} = \sum_{k=1}^2 w_k (\hat{p}_{ik} - \hat{p}_{ck})$, where \hat{p} refers to the estimated proportion.

Two-sided 95% confidence intervals for the difference (based on a normal approximation) are formed by:

$$\hat{d} \pm 1.96 \sqrt{\sum_{k=1}^2 w_k^2 \left(\frac{\hat{p}_{ik}(1 - \hat{p}_{ik})}{n_{ik}} + \frac{\hat{p}_{ck}(1 - \hat{p}_{ck})}{n_{ck}} \right)}$$

In the above formula, the standard error is $\sqrt{\sum_{k=1}^2 w_k^2 \left(\frac{\hat{p}_{ik}(1 - \hat{p}_{ik})}{n_{ik}} + \frac{\hat{p}_{ck}(1 - \hat{p}_{ck})}{n_{ck}} \right)}$. When the number of responders is zero ($x = 0$), then \hat{p} will be replaced by $0.5/(n + 1)$.

The 95% confidence interval for the response rate in each treatment group will also be provided using Wald normal approximation (or the Clopper-Pearson exact method when there are no or all responders in one group).

For the Immunogenicity Sub study, the Clopper-Pearson exact method will be used to compute the associated 95% confidence interval for each treatment, while unconditional exact method proposed by Chan and Zhang will be used to compute the difference in proportions.

090177e19618b8f5\Approved\Approved On: 25-Jan-2021 08:47 (GMT)

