5.3.1. Binary Endpoints

For binary endpoints analyzed at each scheduled visit separately, visit windows (see Appendix 2) will be used to map all observed data into nominal visits. After mapping, for subjects who drop out for any reason, any data will be defined as “non responsive” at all subsequent visits after the last observed value; for other subjects, any observations missing intermittently (including baseline values) will be considered missing completely at random (MCAR) and will remain missing in the analysis.

Additional analyses that are will utilize the longitudinal nature of the binary endpoint. A Generalized Linear Mixed Model (GLMM) will be fit to the observed data (ie, without defining missing data due to dropout as “non-response”). The binary outcome will be modeled using a logistic normal distribution. Fixed factors will include treatment (PF-04965842 200 mg QD and 100 mg QD and the placebo group), visit (Weeks 2, 4, 8 and 12) and treatment by visit interaction. Visit will be modeled as a categorical covariate. A subject specific random intercept will be used to model the correlation within a subject over time (see Appendix 3). Missing observations for the active groups (PF-04965842 200 mg QD and 100 mg QD) will be imputed multiply using a tipping point analysis to estimate the treatment effect under the assumption that the missing data mechanism is missing at random (MAR) or more generally, is missing not at random (MNAR). Using the estimated posterior predictive distribution of the GLMM model parameters obtained using Markov Chain Monte Carlo (MCMC) methods, estimates of the posterior predictive probability of response will be calculated for each treatment group. For subjects with missing data at a visit, the posterior predictive response probability in each active group will

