be re-defined as a weighted linear combination of the posterior predictive response probability from this group and the posterior predictive response probability from the placebo group, where the missing observations in placebo group are assumed to be missing at random (MAR) (see Appendix 3). These weights are fixed MNAR quantities for the active groups. A single imputation of the missing value will be sampled from a Bernoulli distribution with this corresponding shifted/re-defined probability of response for the active groups. This imputation will be repeated multiple times with different MCMC samples to obtain multiple completed datasets. For each such completed dataset, the estimates of the proportions and CMH-weighted difference of proportions between each active group and placebo will be obtained along with the associated standard errors using the methods in Section 5.2.1. Rubin's rule (Rubin, 1987)⁴ will be used to combine the multiple estimates and standard errors across the imputed datasets and provide p-values.

The above analysis can be repeated for different combinations of MNAR quantities which will be applied to the probability of response to assess when the conclusion might change (ie, tipping). Two important scenarios are included in the tipping point analysis framework. When the MNAR quantities are zero and the posterior predictive probabilities in the active dose groups are not shifted, results are obtained under an assumption of MAR for the missing data mechanism. Alternatively, at the other extreme, when the MNAR quantities are 1.0 for each active dose group, results are obtained under an assumption that the distribution of the missing responses after discontinuation of each active group is the same as that of the missing responses on the placebo arm. More detailed descriptions are provided in Appendix 3.

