Appendix 3. A Logistic-normal GLMM for Longitudinal Binary Data and Tipping Point Analysis

Let Y_{ij} be the binary outcome for subject i ($i = 1, 2, \dots, N$) and visit j ($j = 1, 2, 3, 4$). We assume $Y_{ij} = 1$ for a response and $Y_{ij} = 0$ for a non-response. Then we model as:

$$P(Y_{ij} = 1 | x_{ij}, u_i) = \frac{e^{\beta' x_{ij} + u_i}}{1 + e^{\beta' x_{ij} + u_i}} \equiv \pi_{ij}(\beta; u_i)$$

Here, β is a vector of unknown parameters corresponding to the vector of fixed effects x_{ij} and u_i is a subject-specific random effect which is assumed to be normally distributed with mean 0 and variance σ^2 . Note that conditional on u_i , Y_{ij} is independent of Y_{ik} , when $j \neq k$.

The full marginal likelihood of the data is then,

$$L(\beta, \sigma^2) = \prod_{i=1}^N \int_{-\infty}^{\infty} \prod_{j=1}^4 \pi_{ij}(\beta; u_i)^{Y_{ij}} (1 - \pi_{ij}(\beta; u_i))^{(1-Y_{ij})} \times N(u_i; 0, \sigma^2) du_i$$

There is no closed analytical form for this likelihood.

For the present study, the primary endpoint is evaluated at Visit 8 / Week 12 ($j = 4$). There are three treatment groups, so the model term $\beta' x_{ij}$ when written out looks like,

$$\beta_0 + \sum_{k=1}^3 \beta_{1k} \times 1_{(T_i=k)} + \beta_{2j} + \sum_{k=1}^3 \beta_{3jk} \times 1_{(T_i=k)}$$

Here, T_i represents treatment for subject i . The third term in the expression is the effect for visit j and the fourth term in the expression is the interaction effect between treatment and visit. With an overall intercept term, the model is over-parameterized as written and so to fit the model, some restrictions on β are required. The default option (this can be changed using programming syntax) in standard statistical software is to assume $\beta_{13} = 0, \beta_{24} = 0$, thereby interpreting β_{11}, β_{12} as the difference in treatment effect relative to $T = 3$ and $\beta_{21}, \beta_{22}, \beta_{23}$ as the difference in visit effect relative to $V = 4$. Consequently, $\beta_{3jk} = 0$ when $j = 4$ or $k = 3$. So, for example, for a subject taking PF-04965842 100 mg QD at Week 12, the expression would be $\beta_0 + \beta_{11}$. For a subject taking PF-04965842 200 mg QD at Week 12, the expression would be $\beta_0 + \beta_{12}$. For a subject on placebo at Week 12, the expression would be β_0 .

Tipping Point Analysis

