A method to analyze the longitudinal data of a binary endpoint measured during the placebo-controlled period (eg, IGA and EASI-75 response rates at Weeks 2, 4, 8 and 12) under the MNAR assumption is called the tipping point analysis. This tipping point analysis includes two popular scenarios as special cases: (1) the Jump-to-Reference (JTR) analysis in which the response rate for a missing subject assessment in the active treatment group takes

090177e19618b8f5\Approved\Approved On: 25-Jan-2021 08:47 (GMT)

on (ie, jumps to) the rate for the reference or control treatment group and (2) the MAR analysis in which the response rate for a missing subject assessment in each treatment group is based on the posterior predictive response rate for that treatment group alone.

The saturated logit normal GLMM as described above will be used as the imputation model. Estimation of the model parameters will be performed under the Bayesian framework using Markov Chain Monte Carlo (MCMC) methods. We assign a non-informative prior for each component of β to be independent and identically distributed as $\sim N(0, 10000)$ and assign a weakly informative prior for σ^2 as an Inverse-Gamma distribution with shape=1 and scale=1. With this prior distribution, the 90th percentile for σ^2 is approximately 9.

Let $\beta^b, u_i^b, b = 1, 2, \dots, B$ be a sample from the posterior distribution. A single imputation $\widetilde{Y}_{i,j}^b$ of missing Y_{ij} is based on the posterior predictive distribution of the response probabilities estimated from the GLMM. For example, if subject i is randomized to PF-04965842 100 mg QD ($T_i = 1$), then at Week 12 ($V = 4$),

$$\text{logit}(\pi_{i,1,4}^b) = \text{logit} \left(P(\widetilde{Y}_{i,4}^b = 1 | T_i = 1, V = 4) \right) = \beta_0^b + \beta_{11}^b + u_i^b.$$

If subject i is randomized to PF-04965842 200 mg QD ($T_i = 2$), then at Week 12 ($V = 4$),

$$\text{logit}(\pi_{i,2,4}^b) = \text{logit} \left(P(\widetilde{Y}_{i,4}^b = 1 | T_i = 2, V = 4) \right) = \beta_0^b + \beta_{12}^b + u_i^b.$$

If subject i is randomized to placebo ($T_i = 3$), then at Week 12 ($V = 4$),

$$\text{logit}(\pi_{i,3,4}^b) = \text{logit} \left(P(\widetilde{Y}_{i,4}^b = 1 | T_i = 3, V = 4) \right) = \beta_0^b + u_i^b.$$

In the tipping analysis, we apply a series of fixed quantities $\delta = (\delta_1, \delta_2)'$ to account for MNAR. We define,

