$$\begin{aligned} \pi_{i,3,4}^{*b} &= \pi_{i,3,4}^b, \\ \pi_{i,1,4}^{*b} &= \delta_1 \pi_{i,3,4}^b + (1 - \delta_1) \pi_{i,1,4}^b, \\ \pi_{i,2,4}^{*b} &= \delta_2 \pi_{i,3,4}^b + (1 - \delta_2) \pi_{i,2,4}^b \end{aligned}$$

We then sample the single imputed value $\widetilde{Y}_{i,j}^b$ from a Bernoulli distribution with probability of success $\pi_{i,T_i,4}^{*b}$. For the present analysis, the responses from the placebo arm are not shifted.

Analysis of an imputed data set will produce an estimate as well as standard error of the treatment difference using CMH and normal approximation in Section 5.2.1. For a given value of MNAR parameter δ , this is repeated for B (typically, $B=500$) times to generate B complete imputed data sets and these B sets of estimates are combined using the Rubin's Method (Rubin, 1987).⁴ This can then be repeated for different values of MNAR parameter δ to evaluate the impact of missing data. Note that $\delta = (0, 0)'$ corresponds to an

MAR analysis and $\delta = (1, 1)'$ corresponds to an analysis commonly known as Jump-To-Reference (JTR). As a special case, we will consider $\delta_1 = \delta_2$ for our analyses.

090177e19618b8f5\Approved\Approved On: 25-Jan-2021 08:47 (GMT)

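### The imputation model for the supplementary tipping-point analyses leaves out baseline severity, although each imputed data set is then analysed by CMH stratified on it (minor; one-term fix)

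*SAP*

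**What the plan says.** **Imputation model.** SAP 5.3.1 lists the terms: "Fixed factors will include treatment (PF-04965842 200 mg QD and 100 mg QD and the placebo group), visit (Weeks 2, 4, 8 and 12"), and the sentence ends with the treatment-by-visit interaction. It then adds: "A subject specific random intercept will be used to model the correlation within a subject over time". Appendix 3 writes out the linear predictor as intercept, treatment and visit, and says that "the fourth term in the expression is the interaction effect between treatment and visit". There is no fifth term. The appendix confirms the role of this model: "The saturated logit normal GLMM as described above will be used as the imputation model". Saturated there can only mean saturated in treatment by visit.

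**Analysis of the imputed data.** SAP 5.3.1 says that the "CMH-weighted difference of proportions between each active group and placebo will be obtained" from each completed data set. Appendix 3 likewise specifies "the treatment difference using CMH and normal approximation in Section 5.2.1". SAP 5.2.1 defines that test as the CMH "statistic adjusting for baseline disease severity (IGA = 3 or IGA = 4"), with differences formed inside each stratum and then weighted.

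**Where it is used.** Only in the supplementary treatment-policy analyses of the two co-primary endpoints (SAP 6.1.1.2.2 and 6.1.2.2.2). The main analyses (SAP 6.1.1.1 and 6.1.2.1) count dropouts as non-responders and do not use the model.

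**The concern.** An imputation model should contain at least the variables in the analysis applied to its output, and any known predictor of both outcome and missingness. Severity qualifies on the first count. On the second, it bears on the IGA outcome by definition: response needs a score of 0 or 1, so a participant starting at IGA 3 must fall two points and one starting at IGA 4 at least three. The SAP adjusts for severity in its CMH (5.2.1), ANCOVA (5.2.2), MMRM (5.2.3) and log-rank (5.2.5) methods. The binary imputation model is the exception, and no reason is given.

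As written, a moderate and a severe participant in the same arm with the same observed responses receive the same imputed probability. For someone with no post-baseline assessment the random intercept carries no information about severity at all.

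At stake is how well the tipping-point result can be read. Protocol 9.4.2.1 promises both MAR and MNAR analyses. The other supplementary analysis in the SAP, on the per-protocol set, requires observed Week 12 scores. The tipping-point analysis is therefore the only one that varies the missing-data assumption for the co-primary endpoints, and its delta = 0 anchor should not carry an avoidable bias.

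**Working it through.** **1. The plan's own figures.** The plan states no figure for this analysis. Its planning rates set the scale: 75 per arm, IGA 12% v 32%, EASI-75 23% v 53%, two-sided 5%. Pooled-variance power is Φ{[d − 1.96√(2p̄(1−p̄)/n)] / √[(p₁(1−p₁)+p₂(1−p₂))/n]}.
- IGA: (0.20 − 1.96×0.0676)/0.0656 = 1.03, giving 84.8% (plan: at least 80%).
- EASI-75: (0.30 − 1.96×0.0793)/0.0754 = 1.92, giving 97.2% (plan: at least 96%).

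Both reproduce, and neither depends on the imputation model.

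**2. Hand calculation (all inputs assumed).** Shift in one arm's rate = missing × excess severe share among dropouts × response gap between strata / 75.
- 8 missing, excess 0.2, gap 0.15: 8×0.2×0.15/75 = 0.3 points.
- 8 missing, excess 0.3, gap 0.25: 8×0.3×0.25/75 = 0.8 points.
- 12 missing, same upper values: 12×0.3×0.25/75 = 1.2 points.

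The reported quantity is the difference between arms. If both arms have the same dropout pattern, only the difference in gaps remains. With gaps of 0.25 (active) and 0.15 (placebo):
- 8×0.2×0.10/75 = 0.2 points
- 8×0.3×0.10/75 = 0.3 points

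With equal gaps it is zero. This arithmetic ignores what the random intercept recovers from observed visits.

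**3. Model-based illustration.** The logistic-normal model was fitted by maximum likelihood at population level, with and without a severity term. Week 12 was imputed from each subject's posterior, and the stratum-weighted difference was formed. Assumed: severe share 40%, random-intercept SD 2, true Week 12 IGA rates 12% v 32% (difference 20.0 points), one active arm against placebo. Differences are in points; MAR is delta = 0 and JTR (jump-to-reference) is delta = 1.

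| | Severity log-OR | Dropout | MAR, without severity | MAR, with | JTR, without | JTR, with |
|---|---|---|---|---|---|---|
| a | −1.5 | 5% moderate, 20% severe, both arms | 20.2 | 20.0 | 18.1 | 18.1 |
| b | −1.5 | 30% severe placebo, 5% elsewhere | 19.5 | 20.0 | 18.5 | 19.0 |
| c | −1.5 | 10% everywhere | 20.0 | 20.0 | 18.0 | 18.0 |
| d | −3 | 40% severe placebo, 5% elsewhere | 18.8 | 20.0 | 17.8 | 19.0 |
| e | −3 | 40% severe active, 5% elsewhere | 22.5 | 20.0 | 18.6 | 17.8 |
| f | −3 | 5% moderate, 40% severe, both arms | 21.3 | 20.0 | 17.6 | 17.8 |

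Errors at delta = 0 are +0.2, −0.5, 0.0, −1.2, +2.5 and +1.3 points. The sign varies, so the omission is not reliably conservative.

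**4. Strata and the weighted difference.** Omitting severity pulls the stratum rates together. In (e) the severe active rate is imputed as 17.8% against a true 11.0%. In (c) the same happens mildly (21.2% against 20.4%), yet the weighted difference stays at 20.0. Convergence of the strata does not by itself bias the reported result; dropout that depends on severity does.

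**Limits of the illustration.** It uses maximum likelihood rather than the planned MCMC. The model with severity is correctly specified by construction, which is why it returns exactly 20.0.

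**The case against.** The omission itself is not in dispute: Appendix 3 writes the predictor out in full and no other section adds the term. The case against giving it weight is about harm, and most of it stands.

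- **Reach.** A reader might infer that the co-primary results are affected. They are not. SAP Appendix 1 marks the tipping-point rows as not primary, and the main CMH analyses, alpha, sample size and the testing sequence in SAP 5.1 do not use the model.
- **Size.** A reader might take the 0.3 to 1.2 points of step 2 as the bias in the treatment effect. That is the shift in one arm's rate. It carries over in full only if severity-related dropout is confined to one arm. The top of that range may also be impossible for placebo IGA: at 12% overall, a 25-point gap makes the severe rate negative unless the severe share is at least 1 − 0.12/0.25 = 52%.
- **Extremes.** The range of −1.2 to +2.5 points needs a log-OR of −3 and 40% dropout among severe participants. Nothing in the documents supports those values as expected.
- **Participants with nothing observed should be few.** Protocol 7.1 asks for end-of-treatment assessments after stopping treatment, 7.2 for an early discontinuation visit where possible, and the Week 2 window in SAP Appendix 2 runs from Day 2 to Day 22.
- **Delta already spans a larger departure.** With 8 missing and a 20-point effect, going from MAR to jump-to-reference moves the estimate by about 8×0.20/75 = 2.1 points.

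The last argument does not fully dispose of the point. Delta shifts the active arms towards placebo, whereas the omission can push either way and moves the starting point of that scale. In (d), jump-to-reference itself moves from 19.0 to 17.8.

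**Conclusion.** The point holds as a minor one. MAR in the tipping-point analysis is not conditional on the randomisation stratum, although the analysis of the imputed data is stratified on it. The delta = 0 difference is unbiased if dropout is unrelated to severity. Otherwise it can err in either direction, mainly when the dependence differs between arms; case (f) shows that a common pattern can matter too if the severity effect is very strong. Under moderate assumptions the movement is about 0.2 to 0.5 points on a 20-point effect. The confidence is high for the omission and low for any particular size, because dropout rates, severe share and stratum-specific response rates are all assumed.

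**What to change.** In SAP 5.3.1, add baseline disease severity (IGA 3 v 4) to the fixed factors of the mixed model. In Appendix 3, add the matching term to the written-out linear predictor and to the three Week 12 imputation probabilities. The appendix assigns the same prior to every component of β, so no new prior is needed. Use the severity variable already defined in SAP 3.4 and used for the CMH strata. The cost is one model term and a line or two of text. No new data are needed, and power, alpha and the primary analysis do not change.

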5.3.2. Continuous Endpoints

For non-PRO continuous endpoints measured longitudinally, missing values post baseline will not be imputed explicitly. For such endpoints, assuming that the missing data mechanism is missing at random (MAR), the data will be analyzed based on a restricted maximum likelihood (REML) using a linear mixed effect model with repeated measures for these continuous variables (see Section 5.2.3). This model will yield valid inferences in the presence of a missing data mechanism that is MAR.

For the continuous PRO variables such as CDLQI, HADS, POEM, DFI, PtGA, EQ-5D-Y and Peds FACIT-F, rules suggested by the developers of these instruments will be followed in calculating the missing values. If these rules are not enough for imputing a value, then the missing values will be handled in the same way as non-PRO variables.

Only available measurements will be used when taking a simple average for the analysis for a time point (eg, Week 12 PSAAD).

5.3.3. Time to Event Endpoints

For time-to-event endpoints, participants who complete the study without the event of interest or those who withdraw before experiencing the event of interest will have their event times right censored at the last available measurement time (or visit) used to define whether the participant experienced the associated event (ie, the event of interest is presumed to have occurred beyond this time point).

6. ANALYSES AND SUMMARIES

6.1. Primary Endpoint(s)

6.1.1. Week 12 IGA Response

6.1.1.1. Main Analysis

- Estimand strategy: Composite, Estimand 1(Section 2.1.1).
- Analysis set: FAS (Section 4).
- Analysis methodology: CMH and normal approximation in Section 5.2.1.
- Intercurrent events and missing data: The intercurrent event is captured through the variable definition; for participants who drop out for any reason, the response will be defined as “non-responsive” after that point.
- The number of participants, number and percent of response at Week 12 along with the 95% confidence interval by normal approximation will be presented for each treatment arm.
- The CMH test p-value, the estimate of the difference in proportions of response at Week 12 along with the corresponding 95% confidence interval by CMH normal approximation will be presented for each PF-04965842 dose group versus placebo.

6.1.1.2. Sensitivity/Supplementary Analyses

6.1.1.2.1. Supplementary Analysis - PPAS

An analysis that assesses the primary endpoint on the analysis set PPAS (Section 4). It will use the same methodology and summary as the main analysis.

6.1.1.2.2. Supplementary Analysis – Treatment Policy Estimand

- Estimand strategy: Treatment Policy, Estimand 3 (Section 2.1.3).
- Analysis set: FAS (Section 4).
- Analysis methodology: IGA response will be analyzed using a tipping point analysis in Section 5.3.1 including data from Weeks 2, 4, 8 and 12.
- Intercurrent events and missing data: All data collected will be utilized; missing values will be handled through multiple imputations as described by Tipping Point Analysis (Section 5.3.1 and Appendix 3).
- The number of participants, the number and percent of participants with missing response, and the estimate of response percentage at Week 12 along with the corresponding 95% confidence interval will be presented for each treatment arm.

- The estimate of the difference in proportions of response at Week 12 along with the corresponding p value and 95% confidence interval will be presented will be presented for each PF-04965842 dose group versus placebo.

